## 11. ETHICAL CONSIDERATIONS

### a. Ethical Review

All relevant documents must be reviewed and approved by the Ethics Committee and additionally submitted to the relevant authorities in accordance with the guidance of submission and conduct of clinical trials.

The clinical trial shall be performed in full compliance with the legal regulations according to the Drug Law (AMG - Arzneimittelgesetz) of the Republic of Austria.

An application must also be submitted to the Austrian Competent Authorities (Bundesamt für Sicherheit im Gesundheitswesen (BASG) represented by the Agency for Health and Food Safety (AGES PharmMed), and registered to the European Clinical Trial Database (EudraCT) using the required forms. The timelines for (silent) approval set by national law must be followed before starting the study.

### b. Consent Procedures

After a detailed information about the study procedures and study medication, as well as the potentially related risks and benefits, the written informed consent will be obtained from each participant by the principal investigator or a designee. At each site, informed consent will be prepared according to the institutional requirements for informed consents. Consent will be collected by the investigator before patient inclusion in trial and before participating in any study procedure.

One copy of each consent form, signed by the participant and by the investigator, will be given to the patient and the original will be kept by the investigator.

### c. Privacy of patients

All records will be kept confidential. The patient's name will not be released at any time and data sets for each subject will be identified only by the patient enrollment number.

### d. Amendments

Proposed amendments must be submitted to the appropriate Competent Authorities (CA) and Ethics Committee (EC) and approved before the change is implemented. These changes are usually presented in the form of an amendment. Amendments that are intended to eliminate an apparent immediate hazard to subjects may be implemented

SARS-CoV-2 VAC3 study

EudraCT 2021-002348-57

Version 4.0, 10. August 2021

prior to receiving CA/EC approval. However, in this case, approval must be obtained as soon as possible after implementation.

#### e. Insurance

Patients will be covered by a clinical trial insurance. The patients will be insured as defined during their participation in the clinical trial by legal requirements. The investigator of the clinical trial will receive a copy of the insurance conditions of the 'patients insurance'. The sponsor is providing insurance in order to indemnify (legal and financial coverage) the investigator/center against claims arising from the study, except for claims that arise from malpractice and/or negligence. The compensation of the subject in the event of study-related injuries will comply with the applicable regulations. Details on the existing patients insurance are given in the patient information sheet.

Patients will be insured with a national insurance partner. The name and contact details for the insurer will be provided on the informed consent form.

#### f. Regulatory Requirements and GCP

The investigators at all sites are responsible for, and should warrant that the conduct of the study shall be compliant to ICH-GCP, local regulatory requirements with the EC-approved research protocol.

The investigators will ensure, that this study is conducted in full conformance with the principles of the "Declaration of Helsinki" (as amended at the 64th WMA General Assembly, Fortaleza, Brazil, October 2013) and with the national laws and regulations of the country in which the clinical trial is conducted.

#### g. Research Ethics

Patients who will participate on this clinical trial will receive the third SARS-CoV-2 vaccination in a controlled way and will be informed about their antibody results immediately. Knowledge gained from this study may be helpful to determine efficacy of additional SARS-CoV-2 vaccination. Additional risk equates to the risk of blood draw in general. Therefore pain, local irritation, small bruises, local damage of nerves but also dizziness and infections can occur. Assessed data will be stored from the principal

SARS-CoV-2 VAC3 study

EudraCT 2021-002348-57

Version 4.0, 10. August 2021

investigator. Only authorized team members have access to the data. Processing of the data is only performed on password protected computers at the General Hospital Vienna.

## Study Organization

### h. Data Collection and Case Report Form

For each subject enrolled, regardless of the study drug initiation, an CRF must be completed by the investigator or a designated sub-investigator. This also applies to those subjects, who fail to complete the study. If a subject withdraws from the study, the reason must be noted on the CRF. Case report forms are to be completed on an ongoing basis. Entries and corrections will only be performed by study site staff, who have been authorized by the investigator. Entry errors have to be corrected according the ICH-GCP Guidelines.

The entries will be checked by trained personnel (monitor) and any errors or inconsistencies will be checked and corrected immediately.

Data, collected at all visits, are entered into an Excel sheet. The CRFs constitute source documents established before study onset as detailed in the monitoring plan. The Maintenance of the study database will be performed by the Division of Rheumatology of the Medical University of Vienna.

The investigator shall maintain the records of drug disposition and the final CRF's for a minimum of 15 years after the study closure.

### i. Monitoring

The principal investigator will ensure, that the trial will be appropriately monitored by ensuring that all the rights of the subject are adequately protected, that the trial data are accurate, complete and verifiable from source documents and that the conduct of the trial is in compliance with the protocol and its subsequent amendments, with GCP and with applicable regulatory requirements. Monitoring will be performed by a contract research organization:

CW-Research & Management GmbH  
[name]  
[contact]  
[contact]

SARS-CoV-2 VAC3 study

EudraCT 2021-002348-57

Version 4.0, 10. August 2021

Web: [www.cw-rm.com](http://www.cw-rm.com)Email: [[contact]](mailto:[contact])

The sponsor investigator will ensure, that monitoring activities occur following a pre-defined monitoring plan.

The investigators will verify, that for all patients a written informed consent is obtained before each subject's participation in the trial. The investigators will also ensure, that all patients enrolled will be eligible according to the in- and exclusion criteria as defined in the protocol.

The on-site monitors will be responsible for verifying, that the appropriate assurances and certification for training in the protection of human subjects are in place at the site prior to the initiation of the protocol. They will provide education to all site staff regarding the conduct of the study according to good clinical practices (GCP's). The sponsor will be responsible for ensuring, that informed consent has been obtained for each patient. These records will be verified during the monitoring/auditing visits that will be performed by the designated monitor.

Monitoring visits are planned at the beginning, during and at the end of the study according to the monitoring plan.

j. Audit and inspections

All investigators agree to accept audits and inspections by the competent authorities during and after completion of the study. All data and documents may be subject to audits and regulatory inspection.

k. Relevant protocol deviations

All protocol deviations will be listed in the study report and assessed as to their influence on the quality of the study analysis. No deviations from the protocol and of any type will be made without complying with all IRB/EC established procedures in accordance with applicable regulations.

SARS-CoV-2 VAC3 study

EudraCT 2021-002348-57

Version 4.0, 10. August 2021

#### I. Provision and handling for study medication

Vaccine for the study will be provided by the general Vaccination Board of the County of Vienna. Patients will be vaccinated utilizing the Vienna General Hospital Vaccination infrastructure ("Impfstrasse", 4Süd). Study vaccine will be stored as recommended by the manufacturer's instructions.

#### m. Accountability for study medication

The investigator or his/her representative will verify, that study drug supplies are received intact and in the correct amounts. This will be documented with sign and date, as well as the arrival of drugs. All sheets will be kept in the site files as a record of what was received. Additionally, an investigational product accountability log will be documented, including, but not limited to, date received, lot number, kit number, date dispensed, subject number and the identification of the person dispensing the drug.

## 9. STATISTICAL ANALYSIS

### 9.1 Sample size considerations

According to the available number of patients at our Department, including estimates of non-responders to a standard protocol of mRNA vaccination, and expected participation rates, we will attempt to include 68 patients into this trial. Based on a Chi test comparing 3rd mRNA versus vector vaccine, this number of patients will allow to achieve at least 80% power at a minimal detectable difference of 28% (5% of responders in the mRNA vaccine group versus 33% of responders in the vector vaccine group).

For differences smaller than the minimum detectable difference statistical significance will not be possible to claim.

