### 6.5. Randomization Procedure

SARS-CoV-2 VAC3 study

EudraCT 2021-002348-57

Version 4.0, 10. August 2021

The web-based computerized randomization algorithm “Randomizer for Clinical Trials” by the Medical University of Vienna will be used for randomization. Patients will be randomized in a 1:1 ratio between the third dose mRNA SARS-CoV-2 boost (Biontech/Pfizer or Moderna, respective of their initial vaccination compound) and a single dose boost vector SARS-CoV-2 vaccine (AstraZeneca). Randomization will be stratified by presence or absence of B-cell depletion (determined at screening visit).

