### 9.3 Endpoints analysis

[124]

SARS-CoV-2 VAC3 study

EudraCT 2021-002348-57

Version 4.0, 10. August 2021

The primary endpoint (difference in SARS-CoV-2 antibody seroconversion rate by week 4 after vaccination boost at baseline between third mRNA SARS-CoV-2 (Biontech/Pfizer or Moderna) and vector SARS-CoV-2 vaccine (AstraZeneca)) will be analyzed using Chi-squared Test. For the seroconversion rates, 95% confidence intervals will be calculated. All subjects with available antibody responses fulfilling the eligibility criteria will be included in the analysis.

The secondary endpoints (see section 7.3.2) will be analyzed using descriptive statistics.

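### Section 9.1 treats the 28-point detectable difference as a limit below which significance cannot be claimed; it is a power figure, and the sentence is wrong as written

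*Supplement*

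**What the plan says.** The supplement names section 9 of the final protocol (version 4.0) as the final statistical analysis plan.

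- **Section 9.1** sets the size: "we will attempt to include 68 patients into this trial". It claims "at least 80% power at a minimal detectable difference of 28" percentage points, specified as "5% of responders in the mRNA vaccine group versus 33% of responders in the vector vaccine group". The next sentence reads: "For differences smaller than the minimum detectable difference statistical significance will not be possible to claim".
- **Section 6.5** sets equal allocation: "Patients will be randomized in a 1:1 ratio between the third dose mRNA SARS-CoV-2 boost".
- **Section 9.3** names the primary test: the endpoint "will be analyzed using Chi-squared Test". It adds: "For the seroconversion rates, 95% confidence intervals will be calculated". It sets no minimum difference, states no significance level and does not say whether a continuity correction applies.
- **Section 5.1** states a non-directional alternative hypothesis on seroconversion rates, with no threshold.

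**The concern.** A detectable difference is a property of the design: the true effect at which the test reaches a chosen power. The smallest observed difference that gives p<0.05 is a different quantity, and it is clearly smaller here. The sentence in section 9.1 confuses the two.

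It is framed in terms of what may be claimed, so someone could later take it as a condition on the primary result. A significant test with an observed gap under 28 points could then be disputed by pointing to the plan, or the choice between the two readings could be made after the data are seen. A cut-off placed at the assumed true effect is missed about half the time when that assumption is correct, which does not fit the 80% power stated one sentence before.

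**Working it through.** **Inputs.** N = 68, 1:1, so 34 per arm (sections 9.1 and 6.5). Rates 5% and 33% (9.1). Chi-squared test (9.3). Assumed: two-sided alpha of 0.05, from the 95% intervals in 9.3 and the non-directional hypothesis in 5.1. Continuity correction is unstated, so both variants are shown. No dropout is allowed for.

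**1. The plan's power figure.** Pooled normal approximation, mean rate (0.05 + 0.33)/2 = 0.19:

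z = [0.28·√34 − 1.96·√(2·0.19·0.81)] / √(0.05·0.95 + 0.33·0.67) = (1.6327 − 1.0874)/0.5183 = 1.052, so power = 85.4%.

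Enumerating all outcomes of two binomials with n = 34 gives 89.0% for the uncorrected test and 81% with Yates' correction. All meet the stated 80%. (At 30 per arm the normal formula gives 80.5%. At 34 per arm the same formula puts the 80% point at 25.5 points, so under that formula 28 points is not the 80% figure for 68 patients.)

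**2. The sentence read as a statement about observed differences.** X² = N·(|ad − bc| − c₀)² / (n₁·n₂·m₁·m₀), where a and c are the responders in the two arms, b and d the non-responders, m₁ and m₀ the total responders and non-responders, and c₀ = 0 (uncorrected) or N/2 = 34 (Yates).

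Example, 2/34 versus 8/34: |2·26 − 32·8| = 204.
- Uncorrected: 68·204²/(34·34·10·58) = 4.22, p = 0.040.
- Yates: 68·170²/(34·34·10·58) = 2.93, p = 0.087.

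Smallest significant gap for low counts in one arm:

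| Responders in lower arm | Uncorrected | Yates |
|---|---|---|
| 0 | 0 vs 4: 11.8 points, p = 0.039 | 0 vs 6: 17.6 points, p = 0.033 |
| 1 | 1 vs 6: 14.7 points, p = 0.046 | 1 vs 8: 20.6 points, p = 0.032 |
| 2 | 2 vs 8: 17.6 points, p = 0.040 | 2 vs 9: 20.6 points, p = 0.048 |

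A 5% rate in 34 patients is 1.7 responders, so these rows surround the design rate. All lie well below 28 points.

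**3. The sentence read as a statement about true differences.** Probability of p<0.05 when the true difference is 20 points, by enumeration:

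| True rates | Uncorrected | Yates |
|---|---|---|
| 5% vs 25% | 69% | 53% |
| 10% vs 30% | 57% | 44% |
| 20% vs 40% | 46% | 34% |
| 30% vs 50% | 40% | 32% |

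Power is reduced, but significance is far from impossible.

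**4. The sentence applied as a bar on the observed difference.** 0.28 × 34 = 9.52, so the arms must differ by at least 10 responders (10/34 = 29.4 points). At true rates of 5% and 33%:
- P(observed difference of at least 28 points) = 50.0%.
- P(that and p<0.05) = 50.0%, with or without correction.

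The share of trials with p<0.05 but barred from the claim would be 89.0 − 50.0 = 39 points (uncorrected) or 81 − 50 = 31 points (Yates).

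**The case against.** The strongest reply is that this is not a decision rule. The sentence stands under sample size considerations, directly after the power statement. It does not say that the difference is an observed one, and it does not instruct anyone to withhold a significant result. The analysis is defined in section 9.3, which has no minimum difference. The likeliest intent is a clumsy warning that smaller true effects are underpowered. If the sentence were obeyed, it could only suppress a claim. It could not raise the type I error, and it changes neither the sample size, the test nor the analysis set.

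Much of this stands. A reader might infer that the plan contains two binding and conflicting criteria, or that its real power is 50%. The documents do not support that: the 50% applies only if someone enforces the sentence against the observed difference.

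A reader might also infer that a true 20-point difference generally has a better than even chance of significance. That holds clearly only at a 5% base rate without correction. The study summary expects at least 30% of third-dose recipients to respond, so higher base rates are plausible, and there the chance is below one half. Likewise, 89% and 12 points belong to the uncorrected test, a choice the plan does not state.

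The reply does not make the sentence true. It fails for observed and for true differences, under either variant of the test, and nothing elsewhere in version 4.0 corrects it.

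**Conclusion.** Wrong as written, and should be fixed. The sentence misstates what a detectable difference means. With 34 per arm and a two-sided 5% level, results near the design rates are significant from about 12–18 points (uncorrected) or 18–21 points (Yates), and a true 5% versus 25% difference has 69% or 53% power. Read as a rule, the sentence would reduce power at the plan's own alternative from 81–89% to 50%, contradicting the power claim it follows.

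These figures assume alpha of 0.05, full follow-up of 68 patients and, for the power loss, true rates of 5% and 33%. The 50% does not depend on the continuity correction; the starting power and the smallest significant gaps do. The point concerns wording that could affect how the primary result is claimed. It is not evidence that the planned test or sample size is unsound.

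**What to change.** Delete the sentence in section 9.1. Put in its place wording such as: *Statistical significance is judged only by the primary test at the two-sided 5% level. The detectable difference describes power; smaller true differences have lower power.*

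This also supplies the significance level and sidedness that section 9 leaves unstated. The cost is one sentence, with no effect on sample size, trial conduct or patients. It should be settled before the primary analysis, so that no choice between readings remains once results are known.

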### 9.2 Relevant protocol deviations

All protocol deviations will be listed in the study report. Major deviations regarding subjects' safety will lead to withdrawal.

### 9.3 Endpoints analysis

[124]

SARS-CoV-2 VAC3 study

EudraCT 2021-002348-57

Version 4.0, 10. August 2021

The primary endpoint (difference in SARS-CoV-2 antibody seroconversion rate by week 4 after vaccination boost at baseline between third mRNA SARS-CoV-2 (Biontech/Pfizer or Moderna) and vector SARS-CoV-2 vaccine (AstraZeneca)) will be analyzed using Chi-squared Test. For the seroconversion rates, 95% confidence intervals will be calculated. All subjects with available antibody responses fulfilling the eligibility criteria will be included in the analysis.

The secondary endpoints (see section 7.3.2) will be analyzed using descriptive statistics.

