#### Null and alternative hypotheses:

H0: There is no statistical difference in the seroconversion rate between patients receiving a third mRNA vaccination and the patients receiving a second boost with AstraZeneca.

H1: There is statistical difference in the seroconversion rate between patients receiving a third mRNA vaccination and the patients receiving a second boost with AstraZeneca.

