### **7.3.2 Secondary study endpoints**

The secondary endpoints of this study are:

- Overall SARS-Cov-2 antibody seroconversion rate by week 4 after vaccination boost at baseline
- Difference in overall SARS-Cov-2 antibody seroconversion rate by week 4 after vaccination boost at baseline between patient with and without B-cell repopulation.
- Antibody concentrations of SARS-CoV-2 ELISA 4 weeks after vaccination boost at baseline.
- Effect of immunosuppressive comedication on SARS-Cov-2 antibody seroconversion rate by week 4 after vaccination boost at baseline
- Evaluation of cellular immunity before and one week after the vaccination.
- Safety of vaccination boost.

SARS-CoV-2 VAC3 study

EudraCT 2021-002348-57

Version 4.0, 10. August 2021

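### The primary chi-squared test ignores the B-cell stratum used in randomisation: it stays valid but is conservative if B-cell status is prognostic, and a stratified test would recover the lost power

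*Supplement*

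**What the plan says.** All references are to protocol version 4.0, whose section 9 is the statistical analysis plan.

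- Section 6.5 sets the allocation: "Patients will be randomized in a 1:1 ratio between the third dose mRNA SARS-CoV-2 boost" and the vector vaccine. It names one stratification factor: "Randomization will be stratified by presence or absence of B-cell depletion (determined at screening visit").
- Section 9.3 gives the primary analysis. The difference in week 4 seroconversion between the mRNA arm and "vector SARS-CoV-2 vaccine (AstraZeneca)) will be analyzed using Chi-squared Test". It adds 95% confidence intervals for the seroconversion rates. Sections 9.1 to 9.6 name no stratified test, adjusted model or adjusted sensitivity analysis.
- Section 9.1 plans the size with the same unstratified test: "we will attempt to include 68 patients into this trial", giving "at least 80% power at a minimal detectable difference of 28" percentage points ("5% of responders in the mRNA vaccine group versus 33% of responders in the vector vaccine group").
- B-cell status comes back only as a secondary endpoint in section 7.3.2: "Difference in overall SARS-Cov-2 antibody seroconversion rate by week 4 after vaccination boost at baseline between patient with and without B-cell repopulation". That endpoint pools the two arms, and section 9.3 analyses it descriptively.
- The Background (section 3) prefers vaccination at least six months after rituximab so that B cells can recover. The protocol therefore regards B-cell status as relevant to response.

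**The concern.** Stratified randomisation removes chance imbalance in B-cell status between the arms, so the difference between arms varies less from one trial to another. The crude chi-squared test does not use this. Its variance is built from the overall response rate and still contains the variation between strata that the design has removed. If the strata respond very differently, the test statistic is too small on average and the p-value too large.

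What is at stake is efficiency. Section 9.1 ties the sample size to the patients available in the department, so adding patients is not an easy way to gain power. A test that uses the stratification already in place could supply some at no cost.

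**Working it through.** **Inputs.** From the plan: 68 patients at 1:1, so 34 per arm; 5% versus 33%; two strata; non-directional alternative ("H1: There is statistical difference in the seroconversion rate between patients receiving a third mRNA vaccination"), hence two-sided. Assumed: alpha 0.05, which is not stated but agrees with the 95% intervals; the share of depleted patients; response rates by stratum; exact balance of the strata between arms. The documents give none of the last three.

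**1. The plan's own figure.** Power is Φ[(Δ − 1.96·SE₀)/SE₁], with SE₀ = √(2·p̄(1−p̄)/n) and SE₁ = √((p₁(1−p₁)+p₂(1−p₂))/n). Here Δ = 0.28 and p̄ = (0.05+0.33)/2 = 0.19.

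- n = 34: SE₀ = √(0.3078/34) = 0.0951 and SE₁ = √(0.2686/34) = 0.0889, so z = (0.28 − 0.1865)/0.0889 = 1.052 and power is 85.4%.
- n = 30: z = 0.861 and power is 80.5%.
- Exact enumeration at 34 per arm gives 89.0% for the Pearson test and 81% with Yates's correction or Fisher's test.

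The claim of at least 80% is reproduced.

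**2. Why the crude test is conservative.** With equal strata and no vaccine effect, the crude variance uses p̄(1−p̄), while the balanced design has the mean of p_s(1−p_s) over the strata. For 5% (depleted) and 33% (repopulated):

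- crude: 0.19 × 0.81 = 0.1539
- actual: (0.0475 + 0.2211)/2 = 0.1343
- ratio 0.873, square root 0.934
- the effective critical value is 1.96/0.934 = 2.10, so the approximate two-sided rejection rate is 3.6%

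Simulation with 400,000 trials gives 3.8%, in line with this.

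**3. Type I error by simulation**, 34 per arm, no vaccine effect, nominal 5%, no continuity correction:

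| Depleted share | Response, depleted / repopulated | Crude chi-squared | CMH |
|---|---|---|---|
| 50% | 19% / 19% | 5.2% | 4.9% |
| 50% | 10% / 28% | 4.7% | 5.0% |
| 50% | 5% / 33% | 3.8% | 5.1% |
| 50% | 5% / 50% | 2.6% | 4.9% |
| 70% | 5% / 52% | 2.0% | 4.9% |
| 50% | 2% / 60% | 1.3% | 5.1% |
| 50% | 5% / 80% (extreme) | 0.4% | 5.3% |

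Under simple randomisation the crude test rejects 5.1–5.5% in these and similar settings. The small excess over 5% in the first row reflects discreteness, not stratification.

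**4. Power at the planned 5% versus 33%**, marginal rates held fixed, 50% or 70% depleted, stratum odds ratio (OR) varied:

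| Stratum OR | Crude (50% / 70% depleted) | CMH (50% / 70% depleted) | Points lost by the crude test |
|---|---|---|---|
| 1 | 89.1 / 89.0 | 88.9 / 88.8 | none (CMH 0.2 lower) |
| 3 | 89.5 / 89.5 | 89.9 / 90.0 | 0.4–0.6 |
| 6 | 90.1 / 90.2 | 91.3 / 91.9 | 1.2–1.7 |
| 10 | 90.6 / 90.9 | 92.4 / 93.5 | 1.8–2.6 |
| 20 | 91.2 / 92.0 | 93.7 / 95.7 | 2.4–3.7 |

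**5. Power at higher response rates.** The planned rates average 19%, which leaves little room for differences between strata. The study summary, however, expects at least 30% of patients to respond to a third dose. With equal strata and assumed rates (depleted / repopulated):

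| mRNA | Vector | Arms overall | Crude | CMH |
|---|---|---|---|---|
| 5% / 35% | 15% / 75% | 20% v 45% | 63.7% | 73.1% |
| 2% / 30% | 10% / 70% | 16% v 40% | 64.0% | 73.6% |
| 2% / 45% | 10% / 90% | 23.5% v 50% | 70.2% | 88.3% |

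The first row averages (20+45)/2 = 32.5%, in line with the summary. Its stratum odds ratios are about 10 (mRNA) and 17 (vector). In the second row both are 21; in the third they are about 40 and 81, so that row is an extreme case.

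**The case against.** The strongest reply is that nothing in the plan breaks. A reader might infer from the mismatch that the trial's error rate is wrong in the harmful direction. It is not: stratification moves the crude test only downwards from its usual level, so a significant result stands. A reader might also infer that the trial misses its stated power. It does not: section 9.1 plans with the same unstratified test, and at 5% versus 33% that test has 85% power by formula and 89–92% by exact calculation or simulation. Both replies stand.

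A reader might further infer that the planned confidence intervals are too wide. Section 9.3 promises intervals for the seroconversion rates and mentions none for the difference. A CMH test would not change per-arm intervals, so that criticism has no footing.

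The size of the loss is also open to challenge. The larger losses need strong stratum effects and response rates above those in section 9.1, and the documents give neither stratum sizes nor rates by stratum. Section 6.5 states no block size, and the complete-case rule in section 9.4 could loosen the balance; both would bring the crude test back towards 5%. This stands too. In the 20% versus 45% and 16% versus 40% examples, even CMH stays below 80% power, so the choice of test explains only part of the shortfall there.

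What the reply does not remove is that the stratified test costs about 0.2 points if B-cell status proves irrelevant and gains power if it matters.

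**Conclusion.** The point holds as a matter of efficiency, not validity. The primary test leaves out the only stratification factor. If B-cell status is prognostic, the crude test is conservative, with type I error of about 1–4% over most of the assumed scenarios with a clear stratum effect (4.7% when the effect is mild, below 1% when it is extreme). The power forgone is nil without a stratum effect, about 0–4 points at the planned 5% versus 33%, and about 9–10 points or more at assumed higher response rates with strong stratum effects. These figures rest on two-sided alpha 0.05, 34 evaluable patients per arm, exact balance within strata and assumed stratum rates. The direction is firm; the size is not known from the documents. The grade is free improvement.

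**What to change.** In section 9.3:

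- Make the primary test a CMH test stratified by B-cell depletion at screening, using the stratum recorded at randomisation, without continuity correction. State this explicitly, because a correction brings its own conservatism: at 34 per arm and a common 19% response rate, Yates's correction takes the crude test from 5.2% to 2.4%.
- Report the stratum-weighted (Mantel-Haenszel) risk difference with a 95% confidence interval. Section 7.3.1 defines the endpoint as a difference in rates, and a CMH test alone gives no estimate of it.
- Keep the crude chi-squared test as a sensitivity analysis.

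The cost is two or three sentences. No new data, patients or visits are needed, and the sample size stands. The change should be made before the outcome data are analysed, since a switch to a stratified test afterwards could look data-driven.
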